IRB Document Approval Date: 1/15/2019

NCT Number: NCT02206620

Title: Effects of Cholinergic Augmentation on Measures of Balance and Gait

Principle Investigator: [name]

Effects of Cholinergic Augmentation on Measures of Balance and Gait

Abstract. We will compare the effects of placebo and donepezil, a cholinesterase inhibitor that will enhance the effects of nicotinic and muscarinic cholinergic neurotransmission, on measures of standing postural sway, walking variability, and dual-task cost as indices of fall risk in Parkinson's disease (PD) subjects in a double-blind, placebo controlled, cross-over randomized clinical trial. In addition, short-latency afferent inhibition (SAI), a physiological index of central cholinergic function will be measured to determine if the deficits in balance and gait correlate with abnormalities of the SAI and if SAI is altered by donepezil as a measure of drug efficacy. The attention network test will be administered to determine if changes in gait and balance are mediated by changes in attention.

Hypothesis. Cholinergic systems contribute to mobility in Parkinson's disease (PD). Measures of gait and balance will improve in response to cholinergic augmentation with a cholinesterase inhibitor, donepezil.

Aim 1. Examine the effects of a cholinesterase inhibitor, donepezil, on physiological markers of mobility associated with falls in PD (postural sway in stance and gait variability).

Aim 2. Determine the effects of donepezil on dual-tasking during postural sway and gait variability and on attention using the Attention Network Test.

Aim 3. Correlate Short-latency Afferent Inhibition (SAI), a transcranial magnetic stimulation-induced marker of cortical cholinergic tone, with mobility deficits at baseline and with donepezil treatment.

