We examined gait variability during a 2-minute walk in 20 PD subjects and 20 age-matched control subjects as part of an ongoing trial. The coefficient of variation of stride duration and cadence were significantly larger in the PD group. Figure 3 illustrates the variability in stride duration for each stride during a 2-minute walk for a representative subject with PD and an age-matched control subject. The PD subject's stride time was longer (1.04 vs 0.98 sec), representing slower gait and more variable with a larger coefficient of variation (3.26 vs 1.59) than the control subject.

Gait Protocol. Gait control measurements will rely upon the ankle gyroscopes for spatial and temporal gait measures with stride time variability the primary gait outcome. Subjects will walk

at their natural pace down a 20-meter long hallway, turn around at the end and return to the starting point and then continue walking back and forth for two minutes. The 180-degree turns during the walking are automatically detected and analyzed separately by Mobility Lab.

Dual Tasking Unmasks Instability. There is abundant evidence that gait and balance are under cortical control, requiring attention, as demonstrated in studies of gait and balance with concurrent mental tasks (dual-tasking).¹⁷ Dual tasking increases measures of gait instability in patients with PD.¹⁸ These observations indicate that cholinergic drug effects could be mediated by altering the ability to dual task and thereby influencing the risk of falling.

Dual Task Paradigm. The effects of dual tasking on sway and gait variability will be assessed with a mental task of counting backwards by 3s from various starting numbers. While performing the mental task, subjects will wear a small microphone connected to a small, custom-made computer with voice recording to record their performance on the mental task. Responses will be recorded for accuracy. Subjects will perform the counting backwards by 3s as a single task while sitting and then during standing and walking. This will allow calculating the dual-task costs on balance and walking.¹⁸

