Interpretation. We are especially interested in determining whether gait and balance are directly influenced by cholinergic manipulation or whether changes in attention capacity are primarily responsible for changes in balance and gait. If, for example, we find that ability to balance and walk during dual tasking is altered out of proportion to changes during standing and walking without dual tasking, it would suggest that cholinergic systems mainly contribute to attentional capacity required for balance and gait. Because of the evidence linking executive dysfunction with gait disorders, we expect that the executive attention which has been related to falls and to gait may be affected out of proportion to alerting and orienting aspects of attention although Posner and colleagues have linked alerting to cholinergic function.

Privacy, Confidentiality and Data Security. Standard institutional practices will be followed as described in the OHSU Information Security and Research Data Resource Guide (http://ozone.ohsu.edu/cc/sec/isg/res_sec.pdf) to maintain the confidentiality and security of data collected in this study. Study staff is, and will continue to be, trained with regard to these procedures. Paper files will be stored in locked filing cabinets in restricted access offices at OHSU. Electronic data is stored on restricted drives on the OHSU network and on encrypted

computers. Access to data/specimens is restricted to study personnel and requires OHSU ID/password authentication.

Upon enrollment, subjects will be assigned a code that will be used instead of their name, medical record number or other personally identifying information. Electronic files for data analysis will contain only the subject code.

Codes will not contain any part of the 18 HIPAA identifiers (initials, DOB, MRN, etc.)

The key associating the codes and the subjects personally identifying information will be restricted to the PI and study staff. The key will be kept secure on a restricted OHSU network drive in a limited access folder.

Data will be transferred to/from The Michael J. Fox Foundation in files using encryption. The data released to the Michael J. Fox Foundation will include only de-identified (coded) data.

Data Safety Monitoring Plan (DSMP). There are three safety issues.

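### Accuracy is the only score named for the counting task, so slower counting that protects gait or balance could show no mental-task cost, or even an apparent gain

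*Combined protocol and SAP*

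**What the plan says.** All references are to the combined protocol and SAP.

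- **Task and capture (Dual Task Paradigm).** The secondary task is a "mental task of counting backwards by 3s from various starting numbers". Subjects wear a microphone linked to a "custom-made computer with voice recording to record their performance on the mental task".
- **Scoring (same section).** "Responses will be recorded for accuracy". Accuracy is not defined as share correct, number of errors or number correct. Response rate is not mentioned here or elsewhere.
- **Reference condition (same section).** "Subjects will perform the counting backwards by 3s as a single task while sitting and then during standing and walking". The length of the sitting task is not given.
- **Costs named (same section).** "This will allow calculating the dual-task costs on balance and walking". No cost on the mental task is named.
- **Walking time (Gait Protocol).** Subjects walk the hallway, return, and "then continue walking back and forth for two minutes".
- **Use of the results.** Aim 2 reads: "Determine the effects of donepezil on dual-tasking during postural sway and gait variability and on attention using the Attention Network Test". The Interpretation section considers performance under dual tasking changing out of proportion to performance without it, and says: "it would suggest that cholinergic systems mainly contribute to attentional capacity required for balance and gait".
- **Data Analysis.** The mixed model is described without mention of the counting task.

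**The concern.** In a dual task the subject can give ground on either task. The motor side of that trade-off is measured in detail here. The mental side has one named score, and that score is insensitive to one obvious way of giving ground, which is to answer less often. The plan sets no pace for the answers and does not tell subjects which task to put first, so slower counting is open to them.

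The motor dual-task cost can be compared between treatment phases only if the mental load is known in each. If subjects count more slowly while walking on donepezil than on placebo, a smaller gait cost may look like a benefit. If they count faster on donepezil, a real benefit may be hidden. Accuracy need not move in either case. The Interpretation section would then attribute to attentional capacity a change that came from a different division of effort.

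The protocol's own pilot work on attention treats speed and errors as separate dimensions: the caption to Figure 4 reports reaction time and error rate separately, and both Parkinson's groups had longer reaction times than controls. The counting task, as described, keeps only the error dimension.

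**Working it through.** The documents give no counting rate, accuracy or sample size on this point, so there is no planned figure to reproduce. The check is whether the named score can register slowing.

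**Inputs.** From the documents: a walk of 120 seconds, with accuracy as the named score. Assumed: 60 answers while sitting, the same 120 seconds for sitting, and the error shares and amounts of slowing below.

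**Formulas.** Number correct = answers × share correct. Relative cost = (sitting − walking) / sitting.

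**Main illustration: 60 answers sitting, 42 walking**

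| | Share correct, sitting → walking | Errors | Number correct | Change in accuracy | Fall in correct answers |
|---|---|---|---|---|---|
| Same care | 95% → 95% | 3.0 → 2.1 | 57 → 39.9 | 0 points | (57 − 39.9)/57 = 30% |
| Slower and more careful | 90% → 95% | 6.0 → 2.1 | 54 → 39.9 | 5 points better | (54 − 39.9)/54 = 26% |

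In correct responses per second, the first row is 57/120 = 0.475 falling to 39.9/120 = 0.333. An error count does worse than share correct: it improves in both rows, simply because fewer answers were given.

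**Range over the amount of slowing** (sitting: 60 answers, 90% correct, 54 correct)

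| Slowing | Answers | Cost on share correct, error share still 10% | Cost on number correct | Cost on share correct, error share 5% | Cost on number correct |
|---|---|---|---|---|---|
| 10% | 54 | 0% | (54 − 48.6)/54 = 10.0% | −5.6% | (54 − 51.3)/54 = 5.0% |
| 25% | 45 | 0% | (54 − 40.5)/54 = 25.0% | −5.6% | (54 − 42.75)/54 = 20.8% |
| 50% | 30 | 0% | (54 − 27)/54 = 50.0% | −5.6% | (54 − 28.5)/54 = 47.2% |

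The −5.6% is (0.90 − 0.95)/0.90, a cost with the wrong sign. It is the same whether the subject slows by a tenth or by half.

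**Where accuracy does work.** If the rate stays at 60 answers and errors rise from 6 to 12, share correct falls from 90% to 80%, a cost of (0.90 − 0.80)/0.90 = 11.1%. Number correct falls from 54 to 48, also 11.1%. The two scores agree when the rate is unchanged and part when it is not.

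**Between treatments.** Take two rows of the second table with the error share fixed at 10% and the same sitting performance in both phases: slowing of 25% on placebo and 10% on donepezil. The accuracy cost is 0% in each phase, so the treatment difference is nil. On correct answers the costs are 25% and 10%, a difference of 15 percentage points. The motor costs would be compared across phases as though counting had been the same.

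**The case against.** **The sentence describes data capture, and accuracy is undefined.** This stands in part. The text does not say that accuracy is the sole score; that is inferred from no other score being named. If accuracy meant number correct over equal fixed times, slowing would show. But the text does not say so and gives no sitting duration, and under the two ordinary readings, share correct and error count, slowing is missed or reversed.

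**The plan analyses no mental-task outcome, so its score cannot mislead a planned test.** This stands as a limit. Better scoring alone changes nothing unless the score is analysed and read beside the motor costs. It does not remove the point: Aim 2 and the Interpretation section still rest on dual-task results whose mental load is not otherwise described.

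**Rate can be recovered from the recordings, and the study is exploratory.** Both are true, and they make the problem inexpensive to cure. They do not make it harmless, because choosing the counting score after seeing results, among many measures, is what a stated rule prevents.

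**Stronger readings the documents do not support.** A reader might infer that subjects are known to slow down, that the task is formally self-paced, or that a stated power is lost. The documents give no counting data, do not mention pacing, and set no test or power for the counting task. Nor does it follow that the sway and gait dual-task measures are invalid; what is weakened is the explanation attached to them.

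**Conclusion.** The concern holds in this form: the one counting score named is undefined, and under its ordinary readings it cannot register slower counting. In the main illustration it shows no cost, or a 5-point gain, while correct answers fall by 30% or 26%. Over slowing of 10% to 50%, the unseen fall is 10% to 50% with an unchanged error share, and 5.0% to 47.2% if the error share halves from 10% to 5%.

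The insensitivity to slowing is a matter of arithmetic. Its size in this trial is unknown, since every count, error share and amount of slowing above is assumed. How much it matters depends on whether counting rate differs between the donepezil and placebo phases, on which the documents are silent. It affects the reading of Aim 2 and the separation of an attention-mediated from a direct drug effect. It does not affect sway or stride time variability measured without the counting task.

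**What to change.** Replace the scoring sentence in Dual Task Paradigm with:

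*Counting performance is scored from the voice recording as correct responses per second in each condition (sitting, standing, walking), with accuracy reported beside it.*

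A score per second also allows for sitting, standing and walking tasks of different lengths. Two further changes are needed for it to do its work:

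1. In Data Analysis, state that the mental-task cost on this score is analysed in the same mixed model and reported beside the sway and gait dual-task costs.
2. In Interpretation, state that a change in motor dual-task cost is read as attention-related only after the change in counting rate has been considered.

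The rule should be fixed before the treatment code is broken. The cost is slightly more scoring of recordings that are already planned, and one more analysed outcome in an exploratory study that has many. No testing is added.

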forebrain is associated with slower gait⁴ and impairments in working memory, attention and executive function.⁵ In addition, loss of thalamic [¹¹C]PMP, representing loss of PPN cholinergic innervation of the thalamus, is related to falls in PD.⁶ In contrast, the extent of dopaminergic denervation of the striatum evaluated by PET imaging was not correlated with falls.⁶ Finally, neurotoxin lesioning of the cholinergic neurons of the PPN induced gait and postural abnormalities in monkeys.⁷ These observations support the need to examine cholinergic treatments in PD subjects with gait and balance difficulties.

The most direct test of the role of cholinergic systems in postural control to date are two small clinical trials. In a randomized, double-blind, crossover clinical trial of a cholinesterase inhibitor, donepezil, our group found that donepezil reduced falls in PD patients.⁸ An open trial with another cholinesterase inhibitor, galantamine, also reported decreases in falls and freezing of gait (FoG). But these small clinical trials are not conclusive.

Intervention. Cholinesterase inhibitors such as donepezil are standard of care for PD patients with cognitive impairment.⁹ We chose donepezil, an FDA approved drug, because it is possible to create a placebo for the donepezil tablet and it requires only once a day dosing. It is recommended to start donepezil at 5 mg per day to reduce adverse effects (FDA approved drug insert). We will increase the dose to 10 mg/day after 3 weeks, if tolerated, because that is the schedule used in our pilot study and this titration was well tolerated.⁸ Donepezil has a half-life of 70 hours and it requires approximately 15 days to reach steady state. The maximum effects on cognitive measures occur within 3 weeks and loss of effect requires more than 3 weeks and less than 6 weeks (FDA approved drug insert). In our pilot study there were more falls at 3 weeks and 5 mg/day of donepezil than at 6 weeks and 10 mg/day of donepezil and 10 mg was more effective than 5 mg on cognitive measures in PD.⁹ Washout between phases will be 6 weeks to minimize carry-over of effects.

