Protocol. Subjects will be identified for potential recruitment through electronic medical record review; directly through OHSU’s neurology clinics and through IRB approved advertisements. Subjects will receive the first study phase medications from the research pharmacy at the end of the baseline testing. The subject will be called weekly to ask about side effects or problems with the protocol. They will also be asked about falls. These contacts will be captured in case report forms. If there are problems, the investigator will call the subject or the subject will be brought into clinic to evaluate the problem. At 3 weeks, the subjects will have a phone call from one of the neurologists for safety; adverse events will be captured. At 6 weeks, the subject will return to the clinic for repeat testing with the measures captured at baseline and also the subjects will have ANT and SAI testing. The subject will be tested “off” their PD medications.

[figure not shown]

Figure 1. Study design

The subjects will then enter the 6-week washout period. Although the subjects will be on no experimental medications, they will continue to be called weekly to inquire about side-effects,

problems and falls. This is partly done to keep the subject involved in the protocol, as well as to collect data about falls. At the conclusion of the 6 weeks, the subjects will return to the clinic for repeat testing and to have medications dispensed for the final 6-week phase of the protocol. The final 6-week phase will be conducted exactly as was the first six-week phase with repeat testing at the end of the 6 weeks.

Subjects. Subjects will be 30 years or older, of either gender and any racial or ethnic origin. Women who are capable of child bearing must employ birth control. Pregnant women are not eligible to participate. The subjects will have idiopathic Parkinson's disease as determined from history and exam and lack of history or physical findings that would suggest another diagnosis or a parkinsonism-plus syndrome. Subjects may be Hoehn and Yahr stages II to IV. Subjects must be able to stand unassisted for a minute and to walk continuously for 2 minutes without assistance or assistive devices. The subjects must have a Montreal Cognitive Assessment (MOCA) of 23 or above and be judged to be able to appreciate the purpose of the research, give informed consent to participate, be able to cooperate with the testing and be compliant with taking the experimental medications.

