of cholinergic markers, does not have alterations in SAI.²¹ SAI is reduced or abolished by an acute dose of the antimuscarinic agent, scopolamine, in normal individuals. In AD subjects who had reductions in SAI, the response to a single dose of a cholinesterase inhibitor, 3 mg of rivastigmine, predicted the response to long-term anticholinesterase inhibitor treatment; those subjects who had an improvement in SAI with the single dose of cholinesterase inhibitor improved with long-term therapy.²² These observations suggest that SAI may identify subjects in our study who have cholinergic deficits as well as be an indicator of the effects of our cholinergic interventions.

Monitoring Activity at Home. Monitoring activity at home will be accomplished with the small inertial sensors that the subject will be asked to wear on their belt and/or a limb.

Clinical Measures. UPDRS, MOCA, , ABC, PDQ-39 total index and mobility domain subscores and falls recorded during the study will be collected.

Data Analysis. A linear mixed model will be used to analyze a crossover with repeated measures design that includes treatment effects, random effects of treatment sequence within subjects and random effects of subjects within treatments. The observations on each subject are repeated measures (week 0 and 6) under different treatment conditions. Since in a typical experiment using repeated measures, two measurements taken at adjacent times are more highly correlated than two measurements taken several time points apart, we will use Bayesian Information Criterion (BIC) to explore optimal covariance structure for the model. The main focus of the study is to determine how the two treatments outcomes change over time, I.E. time by treatment interaction effect. Generalized least square (GLS) and restricted maximum likelihood (REML) will be used to estimate treatment effects and random effects, respectively. In crossover designs, missing data have much greater influence on the analysis than they would in a parallel groups design especially when missing data are not at random such as drop-outs due to the adverse effects of treatments. We will analyze two separate data sets in order to evaluate the impact of missing/non-response. One data set includes all patients who received at least one study drug and another data set only includes the patients who complete the complete treatment sequence.

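### The crossover model names no period or period-by-week effect, so a week 0-to-6 change that differs between periods costs power and, with unequal sequences, biases donepezil versus placebo

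*Combined protocol and SAP*

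**What the plan says.** The Data Analysis section of the combined protocol and SAP holds the only model specification. The linear mixed model "includes treatment effects, random effects of treatment sequence within subjects and random effects of subjects within treatments". Time is defined thus: "The observations on each subject are repeated measures (week 0 and 6) under different treatment conditions". The target is equally explicit: "The main focus of the study is to determine how the two treatments outcomes change over time, I.E. time by treatment interaction effect".

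Neither of two neighbouring statements supplies a period term:

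- On covariance, the plan reasons that "two measurements taken at adjacent times are more highly correlated than two measurements taken several time points apart" and concludes that "we will use Bayesian Information Criterion (BIC) to explore optimal covariance structure for the model". This concerns variances and correlations, not means.
- The Intervention section says "Washout between phases will be 6 weeks to minimize carry-over of effects". That addresses carry-over, which is a different problem from a period effect.

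The Protocol section shows that period 2 has its own start-of-phase measurement: "At the conclusion of the 6 weeks, the subjects will return to the clinic for repeat testing and to have medications dispensed". There are therefore four test visits, two per phase.

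Two data sets are planned. The first is described as "One data set includes all patients who received at least one study drug"; the second is restricted to completers. The Abstract calls the trial randomised but gives no allocation ratio or blocking.

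**The concern.** In a two-period crossover, each subject's donepezil-minus-placebo contrast is also a contrast between periods, with its sign set by the sequence. If the model has no period effect, any period difference left in the contrast goes into the residual and, when the sequences differ in size, into the estimate as well.

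The second start-of-phase test helps. In completers, a shift that raises or lowers weeks 0 and 6 of period 2 equally drops out of the change. Two things remain:

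1. A week 0-to-6 change that differs between periods. Practice on backward counting is one route: gains may be larger in the first phase than in the second.
2. Any period shift in an outcome compared only at week 6. The Attention Network Test may be one, because the Protocol section adds it to the baseline measures at the 6-week visit.

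The random sequence-within-subject term does not help. Each subject has one sequence, so the term is aliased with subject and cannot absorb a difference in period means.

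What is at stake is a missed drug signal or a shifted estimate. Equal sequences are not assured: no blocking is stated, and Data Analysis itself anticipates drop-out from adverse effects.

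**Working it through.** **Inputs.** The documents give the design, the model terms, the time points and the target contrast. They give no sample size, SD, alpha, allocation ratio, drop-out rate or period effect, so there is no planned figure to reproduce. Assumed for illustration: about 40 subjects, two-sided 5% test, true effect 0.45 SD, period difference 0.25 to 1.0 SD. The unit is the SD of the paired change difference d.

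**Bias.** Let d be the week 0-to-6 change on donepezil minus that on placebo, τ the true effect, and π the period 2 change minus the period 1 change. Then:

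- donepezil first: E[d] = τ − π
- placebo first: E[d] = τ + π
- pooled without period terms: bias = π × (n placebo-first − n donepezil-first)/N

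The absolute bias per unit of π is:

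- 20/20: 0
- 22/18: 4/40 = 0.10
- 18/14: 4/32 = 0.125
- 24/16: 8/40 = 0.20
- 20/12: 8/32 = 0.25

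Exact generalised least squares on the four-visit layout gave 0.100, 0.200 and 0.250 at 22/18, 24/16 and 20/12 under three random-effects covariances. Adding a period main effect alone left these unchanged. Adding period-by-week made them 0, as did a four-level visit factor.

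**Standard error.** With share s donepezil-first, the SE is multiplied by √(1 + 2s(1−s)π²) if a subject's two changes are treated as independent, or by √(1 + 4s(1−s)π²) if they are treated as paired. The plan does not fix which. At s = 0.5 and π = 0.5 these are √1.125 = 1.06 and √1.25 = 1.12.

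**Equal sequences, 20/20** (simulation, 40,000 replicates per cell; independent / paired):

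| π (SD) | SE increase | Power for 0.45 SD | Type I error |
|---|---|---|---|
| 0 | 0 | about 80% | 5% |
| 0.25 | 2% / 3% | 79% / 77% | 4.9% / 4.6% |
| 0.5 | 6% / 12% | 77% / 72% | 3.8% / 2.9% |
| 1.0 | 22% / 41% | 66% / 49% | 1.6% / 0.6% |

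**Unequal sequences**, type I error (independent / paired):

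| Split | π = 0.5 | π = 1.0 |
|---|---|---|
| 22/18 | 4.7% / 3.7% | 4.1% / 1.8% |
| 18/14 | 4.9% / 3.8% | 4.5% / 2.0% |
| 24/16 | 7.6% / 6.1% | 13.0% / 6.7% |
| 20/12 | 8.8% / 7.1% | 16.3% / 8.6% |

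Type I error therefore rises only when the imbalance is marked. Power suffers sooner: at 22/18 and π = 0.5, with the bias opposing donepezil, it is 66% / 61%, against 80% / 79% with the terms. With period and period-by-week terms, bias is 0 and type I error about 5% throughout.

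**How likely is imbalance?** Unblocked randomisation of 40 gives 24/16 or wider in 27% of trials. A fixed 20/20 with 20% drop-out gives a median completer gap of 2, and a gap of 4 or more in 16%.

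**Other cases.** In the all-treated set, with 4 of 20 per sequence stopping on donepezil before week 6, the bias is 0.03 to 0.05 times π even though sequences start equal; it is 0 with the terms. For an outcome compared only at week 6, the paired figures apply, with the SD of the paired week-6 difference as the unit.

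**The case against.** The strongest reply is that the omission is inferred from a brief narrative. The list of model terms leaves out time and time-by-treatment too, yet the latter is soon named as the main focus. The covariance rationale speaks of measurements several time points apart, which makes little sense with two levels of time. If time means four serial visits, period and period-by-week are already covered. This part stands as an ambiguity: the text does not settle the coding. But the explicit weeks 0 and 6 favour two levels, the serial-visit remark concerns covariance only, and a period term is named nowhere.

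Second, no evidence of a period effect is offered. That is true. Practice is less plausible for a two-minute walk at natural pace, which supplies the primary gait outcome, and the counting task varies its starting numbers. At π = 0.1 SD the SE rises by 0.5% or less, and the 1.0 SD case exceeds twice the assumed drug effect. The study is also declared exploratory. These points limit the likely size; they are not a reason to leave the terms out.

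Third, the bias formula depends on the covariance. Under first-order autoregression over visits, the bias at 24/16 is 0.193 per unit of π rather than 0.200; under one arbitrary unstructured covariance it is 0.181, and a stable shift need not cancel exactly. The differences are small, and the added terms still remove the bias.

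**Conclusion.** The concern holds, as a cheap improvement. Confidence is high that the plan names no period or period-by-week effect; the sizes are illustrative because every quantity that drives them is absent from the documents. Fitting the terms as listed, with time at two levels, gives an unbiased but conservative test when sequences are equal, and a biased estimate, in either direction, when they are not. The loss is negligible for a small period difference and material from about 0.5 SD. It matters most for dual-task counting and the Attention Network Test, where practice is plausible. If the team already intends time as a four-level visit factor, only the wording needs to change.

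**What to change.** Replace the fixed-effects wording in Data Analysis with text such as:

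> Fixed effects are treatment, period, week (0 or 6 within phase), treatment-by-week (the primary contrast) and period-by-week. Time means week within phase. A subject random effect is retained and BIC selects the remaining covariance. For an outcome compared only at week 6, the fixed effects are treatment and period, with a random subject effect. The same fixed effects apply in the all-treated and completer data sets.

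A period main effect alone is not enough for the week 0-to-6 contrast. Coding time as a four-level visit factor, with treatment and treatment-by-week, is equivalent. The plan should also state the sequence allocation ratio and whether randomisation is blocked.

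The cost is SAP wording and about two degrees of freedom. If there is no period effect, the SE is multiplied by 1/√(4s(1−s)): nil at 20/20, 0.5% at 22/18, about 2% at 24/16 and about 3% at 20/12. No visit or procedure changes.
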